6.1 Visit 1 (Baseline/Pre-Treatment)

6.1.1 Screening and Enrollment

Patients meeting all inclusion and no exclusion criteria will be offered the opportunity to participate in this study. Patient informed consent will be obtained prior to any study specific procedures and patients will be provided with ample time and opportunity to ask about the details of the study, and decide whether or not to participate.

801 **6.1.2** Medical History

A full medical history will be taken during the baseline visit. Medical history includes previous bariatric and non-bariatric surgeries, and recent & lifetime health history.

6.1.3 Demographics

At baseline, the following demographic data will be collected and recorded: gender, date of birth, and race/ethnicity.

6.1.4 Physical Examination / Clinical Assessment

During the baseline and all in-office follow-up visits, a physical examination will be performed and the following data will be collected and recorded:

- Blood pressure
- Heart rate
- Height (only at baseline)
- Weight
- Waist and neck circumference
- Medications

6.1.5 Diet and Physical Activity Counseling

- Initial nutritional assessment by RD (Registered Dietician)
 - 24 hr diet recall (see attachment)
- Body composition (Basic metabolic rate, % total body fat, % body water weight, muscle mass weight)

6.1.6 Comorbidities Assessment

Comorbidity status will be assessed at baseline. The following co-morbid conditions will be assessed: diabetes, hypertension, and STOP-BANG score.

823 824 825

826

827

816

817

818

821

822

Diabetes Scale

Score	Description
0	Fasting blood glucose (<100 mg/dL)
1	Fasting blood glucose ≥100-125 mg/dL or diabetes, no medications
2	Fasting blood glucose ≥126 mg/dL or diabetes treated with medication (oral and/or
	injectable)

Number of medications:

Hypertension Scale

	Description
0	Normal BP, no indication of hypertension (BP below 120/80 mmHg), no medication
1	Prehypertension (systolic BP 120-139 or diastolic BP 80-89 mmHg), no medication
2	Stage 1 hypertension (systolic BP 140-159 or diastolic BP 90-99 mmHg) or
	hypertension controlled with single medication
3	Stage 2 hypertension (systolic BP ≥160 mmHg or diastolic BP ≥ 100 mmHg) or
	hypertension controlled with multiple medications
4	Hypertension poorly controlled despite multiple medications

828 829

STOP-BANG score:

1.	Do you snore loudly (louder than talking or loud enough to be heard	Yes	No
	through closed doors)?		
2.	Do you often feel tired, fatigued, or sleepy during daytime?	Yes	No
3.	Has anyone observed you stop breathing during your sleep?	Yes	No
4.	Do you have or are you being treated for high blood pressure?	Yes	No
5.	BMI >30kg/m2	Yes	No
6.	Age >50	Yes	No
7.	Neck circumference >16 inches	Yes	No
8.	Male	Yes	No

830

831

832

833

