
516517

We hypothesize that the liraglutide group will demonstrate greater improvement

in cardiovascular risk profile (as assessed by serum lipids, HbA1c, and waist

518	circumference) and quality of life (as assessed by the PHQ-9) at 12 months, than
519	the placebo group.
520	 To evaluate the safety of liraglutide in post-RYGB subjects.
521	o We will monitor adverse events, blood counts and serum chemistries in subjects
522	receiving liraglutide or placebo over a period of 12 months.
523	We hypothesize that the liraglutide group will exhibit more frequent
524	hypoglycemia and elevations in lipase and amylase, but that these episodes will
525	be clinically insignificant.
526	• To evaluate the changes in obesity-related comorbid conditions in patients who are experiencing
527	weight regain following RYGB.
528	 We will monitor obesity-related comorbid conditions in subjects receiving liraglutide or
529	placebo over a period of 12 months.
530	 We hypothesize that the liraglutide group will exhibit improvements in obesity-
531	related comorbid conditions (hyperglycemia, hyperlipidemia, blood pressure, and
532	obstructive sleep apnea) at 12 months, than the placebo group.
533	3.2 Endpoints
534	• Primary Endpoint: Proportion of subjects losing at least 5% of enrollment body weight at 12 months.
535	• Secondary Endpoints: Fasting serum glucose, HbA1c, LDL-cholesterol, HDL-cholesterol,
536	triglycerides, waist circumference, blood pressure, STOP-BANG score, PHQ-9
37	• Primary and secondary endpoints will be assessed at clinic visits prior to randomization and at 3, 6, 9
538	and 12 months post-first study drug administration.
539	3.3 Study Type
540	Randomized, single-center, double-blind, placebo-controlled study with two arms. Randomization will
541	be 2:1 (drug:placebo) with stratification by gender and percent post-operative TBWL (25%, 25 – 49.9%).
542	3.4 Rationale for study Design
543	A randomized, placebo-controlled study design was chosen as this is the methodology that will best
544	assess the efficacy of liraglutide for weight loss in the post-RYGB population. 2:1 randomization was
545 546	chosen with the intention of increasing potential participant interest given better than even odds of
547	randomization to liraglutide.
548	A single-center study was chosen given that the NYU Langone weight management program has a pool
549	of 700 post-RYGB patients in our retrospective database, and that recent data from our program suggests

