550	that 80 % of patients at least 18 months status-post RYGB exhibit regain of ≥10% of maximum post-
551	surgical TBWL – our program has a potential subject pool of 560. We estimate that at least 50% of 560
552	will be eligible for and agree to participate in the study, which will allow us to be able to enroll adequate
553 554	subjects from our program alone. In addition, approximately five post-RYGB patients are referred to our program monthly for evaluation of weight regain. In the case that subject recruitment falls short of goals,
555	we would expand recruitment using advertisements.
556	3.5 Primary Study Endpoints
557	Proportion of subjects losing at least 5% of enrollment body weight at 12 months.
	-r

Universal Trial Number: U1111-1178-7319 Version 7: 10/11/2019 Page 15

557

558	3.6 Secondary Study Endpoints
559 560 561	Fasting serum glucose, HbA1c, LDL-cholesterol, HDL-cholesterol, triglycerides, waist circumference, blood pressure, STOP-BANG score, PHQ-9, Obesity-related co-morbidities assessment
562 563	Primary and secondary endpoints will be assessed prior to randomization and at clinic visits at 3, 6, 9 and 12 months post-first treatment administration.
564	3.7 Primary Safety Endpoints
565 566	The primary safety endpoint is the percentage of patients who are experiencing AEs during 12 months of the trial.
567 568 569 570 571 572 573 574	 3.7.1 Assessments for Safety BMP (Fasting glucose) Amylase Lipase Pregnancy Test (Only applicable for women of childbearing potential) Heart Rate PHQ-9 Current medication list review
575	• Adverse event assessment including symptomatic hypoglycaemia for Type 2 DM patients
576	4 Subject Selection and Withdrawal
577 578	4.1 Number of the subjects: 132 Subjects will not be replaced if they withdraw or become ineligible.

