579 580 581 582 583 584 585 586 587 588	4.2 Rationale for study population The Roux-en-Y gastric bypass (RYGB) is not only the most common bariatric procedure, but also the gold standard to which all others are compared. The average weight loss after RYGB is approximately 35% total body weight. However, the majority of patients who undergo this procedure experience weight regain and thus are at risk of, or re-acquire co-morbid conditions, such as Type 2 diabetes mellitus or hypertension. Revisional surgery, which is the most common treatment for weight regain after bariatric surgery, is often thwarted by resistance from insurance companies, leaving patients with only diet and behavioral change as an option. Due to the fact the GLP-1 agonism plays a significant role in weight loss after RYGB, liraglutide is thought to be a promising adjunct to the long-term treatment plan in patients who experience weight regain after RYGB.
589	4.3 Inclusion Criteria
590 591 592 593 594 595 596	 >18 years who are deemed medically stable ≥18 months status-post RYGB at time of enrollment BMI of ≥30 kg/m² or ≥ 27 kg/m² in the presence of at least one weight-related comorbid condition Regain of ≥10% of maximum TBWL post-RYGB Ability to provide informed consent before any trial-related activities Express willingness to provide signed informed consent and follow protocol requirements
597	4.4 Exclusion Criteria
598	• BMI of $>45 \text{ kg/m}^2$

• Pregnancy at time of enrollment

600

604

605 606

607

608

609

610

613

614

622

623

624

625

626 627

628

629 630

631

632 633

634

635 636

637

638

639

640 641

642

643

644

645

- Intention of becoming pregnant or breast feeding in the next 12 months
- Females of childbearing potential who are not using adequate contraceptive methods
- Presence of acute psychiatric problems or immaturity which would compromise cooperation with the study protocol
 - Presence of biliary disease
 - Known or suspected allergy to liraglutide or any product components
 - Personal or family history of medullary thyroid carcinoma or multiple endocrine neoplasia syndrome type 2
 - History of pancreatitis
 - History of alcoholism
 - History of Type 1 DM (Diabetes Mellitus)
- History of previous bariatric surgery other than RYGB except h/o LAGB and band removal.
- >10 years status-post RYGB
 - < 25% TBWL at post-RYGB weight nadir
 - >50% post-operative TBWL at time of screening
- Simultaneous use of any weight loss medications

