6.1.7 Blood work (total 25 ml blood collection)

- Blood Pregnancy (Total Beta Quantitative HCG) (Only applicable for women of childbearing potential)
- Fasting BMP
- HbA1c
- Lipid profile
- Amylase
- **•** Lipase

839 Additional 15 ml blood for future analyses - Banking of additional plasma and serum for future markers of caridometabolic risk in post-RYGB patients. 840 841 Collecting additional blood for future analysis is mandatory because it is imperative that the stored sample be used for continued analyses as new scientific discoveries are available and for retesting 842 843 during the course of the study if necessary. Samples will be stored in the Bell Vascular Biology Research Program (NYU Smilow 7th floor) 844 845 and accessed only by the study team members. The unique code number that is used to label the 846 samples will not be based on any subject's identifiers. The master list linking names to code 847 numbers will be kept into the password-protected REDCap data management system. 848 Results from these analyses will be preliminary, and the clinical implications of any findings may not be understood for years. Therefore, individual study results will not be shared with the 849 850 851 No genetic testing will be done on the stored samples. Some of the stored de-identified samples may be sent to other places to study the related diseases 852 and conditions. 853 All samples will be destroyed no more than twenty years from the end of the study. However, if 854 855 the subject requests to destroy the stored samples, the study team will destroy the samples upon 856 receiving your written request. 857 858 6.1.8 **Questionnaires** PHQ-9 (see attachment) 859 IPAO (see attachment) 860 861 6.2 Visit 2, 3, 4 (Post-treatment) 862 863 6.2.1 **Physical Examination / Clinical Assessment** 864 During the baseline and all in-office follow-up visits, a physical examination will be performed and the 865 following data will be collected and recorded: Blood pressure 866 Heart Rate 867 Weight 868 Waist and neck circumference 869 Medications 870 871 6.2.2 **Diet and Physical Activity Counseling** 872 Follow up diet and physical activity counseling by RD 873 Collection of diet and exercise diaries (see attachment) Body composition (Basic metabolic rate, % total body fat, % body water weight, muscle mass 874 875 weight) 6.2.3 **Comorbidities Assessment** 876 877 The following co-morbid conditions will be assessed: diabetes, hypertension, and STOP-BANG score at the 3, 6, 9 and 12 month visits. 878 879 6.2.4 **Blood work** 880 Total 10 ml blood collection for visit 2 and 4 Total 25 ml blood collection for visit 3 and 5 881

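### Sleep apnoea is judged only by the STOP-BANG score, whose BMI item falls with weight loss alone; report the change also without the weight-dependent items and by item

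*Combined protocol and SAP*

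**What the plan says.** The fourth aim in section 3.1 predicts that the liraglutide group will improve in "related comorbid conditions (hyperglycemia, hyperlipidemia, blood pressure, and" "obstructive sleep apnea) at 12 months, than the placebo group". The list of secondary endpoints in section 3.6 includes "waist circumference, blood pressure, STOP-BANG score, PHQ-9, Obesity-related co-morbidities assessment".

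At baseline, section 6.1.6 specifies: "Comorbidity status will be assessed at baseline. The following co-morbid conditions will be assessed: diabetes, hypertension, and STOP-BANG score". Section 6.2.3 repeats the assessment: "diabetes, hypertension, and STOP-BANG score at the 3, 6, 9 and 12 month visits". Diabetes and hypertension each have a graded severity scale in 6.1.6. Sleep apnoea has only the STOP-BANG questionnaire. The procedures and the visit schedule contain no sleep study and no apnoea index.

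The eight items are three sleep symptoms (snoring, tiredness, observed apnoea), high blood pressure, BMI above 30, age above 50, "Neck circumference >16 inches", and male sex. Entry under section 4.3 requires a BMI of at least 30, or at least 27 "in the presence of at least one weight-related comorbid condition". Section 4.4 excludes a BMI above 45.

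Section 7.2 compares change in continuous secondary outcomes between arms by t-test, with an ANCOVA on the stratification variables. It gives no item-level analysis and no version of the score without the BMI item. It also says that these results are descriptive because power is limited.

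**The concern.** The drug under test reduces weight, and the score includes a weight threshold that coincides with the main BMI limit for entry. A subject just above BMI 30 who loses a few per cent of body weight drops one point on STOP-BANG even if snoring, tiredness and observed apnoea are exactly as before. More subjects are expected to do so on liraglutide than on placebo. The comparison of change is therefore pushed in one direction before any effect on sleep is considered. Part of the secondary endpoint repeats information that the primary endpoint already carries.

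Two further items may behave in the same way. Neck circumference can shrink with body weight, and the blood-pressure item overlaps an outcome that the plan already measures twice (blood pressure itself and the hypertension scale).

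At stake is a secondary conclusion. Section 3.1 names the disease, but the instrument mixes symptoms of the disease with body size. A favourable difference could be written up as improved sleep apnoea although no sleep item had moved.

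**Working it through.** **The plan's own figures.** The plan states no figure for STOP-BANG. Its sample size for the primary endpoint does reproduce: 27.1% vs 63.2%, two-sided alpha 0.05 (sidedness assumed), power 0.90, 2:1 allocation and a continuity correction give 33 + 66 = 99, and 99/0.75 = 132. Nothing below alters that.

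**Inputs from the protocol.** Mean losses of 8.0% (liraglutide) and 2.6% (placebo), and of 6.2% and 0.2% in a second trial, both cited in section 1.1. Entry BMI of 27 to 45 from 4.3 and 4.4. Baseline BMI of 38.2 ± 6.4 in the planning trial, section 7.1.

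**Assumptions.** The baseline BMI of this post-bypass population is not given. Three normal distributions truncated to 27–45 are used: 38.2 ± 6.4 (the planning trial), 36 ± 5 and 34 ± 4.

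**Step 1: who crosses the threshold.** With proportional loss L, the item turns from yes to no for a baseline BMI above 30 and up to 30/(1 − L).
- Liraglutide: 30/(1 − 0.080) = 32.6.
- Placebo: 30/(1 − 0.026) = 30.8.

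**Step 2: effect on the score.** If every subject loses the arm mean, the mean change in the item is minus the share of subjects in the band.

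| Baseline BMI (assumed) | Share above 30 | Liraglutide | Placebo | Difference |
|---|---|---|---|---|
| 38.2 ± 6.4 | 92.7% | −0.112 | −0.029 | −0.083 |
| 36 ± 5 | 91.4% | −0.144 | −0.037 | −0.108 |
| 34 ± 4 | 87.6% | −0.214 | −0.055 | −0.158 |

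(Differences were taken before rounding.) Letting individual loss vary, with an assumed SD of up to 6.7 percentage points, gives −0.083 to −0.089, −0.108 to −0.111 and −0.151 to −0.158 in the three rows. The second cited trial (6.2% vs 0.2%) gives −0.079 to −0.152 over the same settings. In round terms the item contributes 0.08 to 0.16 points out of 8, always in favour of liraglutide.

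**Step 3: effect on the planned test.** Trials were simulated with 88 vs 44 subjects (132 split 2:1). The SD of loss was 6.7 points, each symptom item was answered yes by 40% of subjects, and symptom answers changed at random in 0, 5 or 10% of subjects, equally in both arms (all assumed). The remaining items were held constant. There was no treatment effect on any sleep item. Share of trials in which the t-test on change was significant at 0.05:

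| Baseline BMI | 0% random change | 5% | 10% |
|---|---|---|---|
| 38.2 ± 6.4 | 28% | 14% | 10% |
| 36 ± 5 | 36% | 20% | 14% |
| 34 ± 4 | 48% | 30% | 23% |

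With 66 vs 33 subjects the range is about 9% to 38%. With equal weight loss in both arms the rate was 5.1%, so the excess comes from the BMI item. The 0% column is an extreme, since real questionnaire answers vary.

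**Step 4: the fixed items.** Sex does not change, so its contribution to a change score is zero in both arms. Crossing age 50 adds a point at a rate that randomisation should balance. These items limit how far the score can fall, but they create no difference between arms.

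**The case against.** The strongest reply is that little hangs on this. STOP-BANG is one of several secondary endpoints, section 7.2 calls those results descriptive, and the endpoint is listed under its own name; sleep apnoea as an outcome appears only in the wording of one hypothesis. The shift is a fraction of a point on an eight-item score. All of that stands, and it is why the point is minor. It does not remove the bias: a descriptive estimate with a built-in shift is still shifted, and 3.1 invites the reader to read it as an effect on the disease.

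Some stronger readings are tempting, and the documents do not support them.
- A reader might infer that the endpoint merely re-measures weight. Three of the eight items are sleep symptoms, and weight loss may truly improve sleep apnoea. The score cannot separate that benefit from a threshold crossing, which is a narrower complaint.
- A reader might suppose that a large share of subjects start just above the cut-off, say 20% to 30% between BMI 30 and 31.6, where a 5% loss is enough (30/0.95 = 31.6). The three assumed distributions put only 6% to 12% there. Multiplying by the planned responder difference of 36.1 points gives 0.02 to 0.04, which is less than in step 2 because that product ignores losses beyond 5%.
- A reader might infer that unrecorded CPAP use favours liraglutide. CPAP appears only in the abbreviation list, and nothing in the documents says which arm would start it more often. If weight loss reduced the need for it, the bias would run against the drug.
- A reader might want apnoea statements to rest on the three symptom items alone. Tiredness can also move with the fatigue (7.5%), asthenia (2.1%) and insomnia (2.4%) listed as drug risks in 1.6.1, and the plan offers no basis for such a sub-score.

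**Conclusion.** The point holds at minor severity. The plan frames a hypothesis about obstructive sleep apnoea and tests it only with a score that contains a BMI threshold. That item alone is expected to move the between-arm difference by about 0.08 to 0.16 points in favour of liraglutide with no change in any sleep symptom.

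The size rests on the cited mean losses carrying over to this population and on the assumed baseline BMI; the nearer the population sits to BMI 30, the larger the shift. The rejection rates in step 3 depend further on assumed symptom prevalence and answer variability, and serve only to show that the shift need not stay invisible in a significance test. The neck and blood-pressure items could add to it, but the documents give no figures to size them. The calculation also takes the score to be the eight-item total, which is the natural reading because no other scoring is described.

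**What to change.** In sections 3.6 and 7.2, keep the STOP-BANG score as the endpoint and add two reports:
- the between-arm change in the score with the BMI and neck-circumference items left out;
- a table of all eight items by arm at baseline and at each follow-up visit.

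State in 7.2 that improvement in sleep apnoea will not be claimed if the difference is confined to the BMI, neck or blood-pressure items. In 3.1, reword the hypothesis from improvement in obstructive sleep apnoea to change in a sleep-apnoea risk score.

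The cost is a few lines of protocol and analysis-plan text. The item answers are already collected at baseline and at every follow-up clinic visit, so no visit, test or subject is added. There are two drawbacks: a score with items removed is not the standard instrument and should be labelled as a sensitivity analysis, and the permitted claim becomes more modest. Recording CPAP use at each visit would help interpretation, but it is optional and this point does not depend on it.

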6.1.7 Blood work (total 25 ml blood collection)

- Blood Pregnancy (Total Beta Quantitative HCG) (Only applicable for women of childbearing potential)
- Fasting BMP
- HbA1c
- Lipid profile
- Amylase
- **•** Lipase

839 Additional 15 ml blood for future analyses - Banking of additional plasma and serum for future markers of caridometabolic risk in post-RYGB patients. 840 841 Collecting additional blood for future analysis is mandatory because it is imperative that the stored sample be used for continued analyses as new scientific discoveries are available and for retesting 842 843 during the course of the study if necessary. Samples will be stored in the Bell Vascular Biology Research Program (NYU Smilow 7th floor) 844 845 and accessed only by the study team members. The unique code number that is used to label the 846 samples will not be based on any subject's identifiers. The master list linking names to code 847 numbers will be kept into the password-protected REDCap data management system. 848 Results from these analyses will be preliminary, and the clinical implications of any findings may not be understood for years. Therefore, individual study results will not be shared with the 849 850 851 No genetic testing will be done on the stored samples. Some of the stored de-identified samples may be sent to other places to study the related diseases 852 and conditions. 853 All samples will be destroyed no more than twenty years from the end of the study. However, if 854 855 the subject requests to destroy the stored samples, the study team will destroy the samples upon 856 receiving your written request. 857 858 6.1.8 **Questionnaires** PHQ-9 (see attachment) 859 IPAO (see attachment) 860 861 6.2 Visit 2, 3, 4 (Post-treatment) 862 863 6.2.1 **Physical Examination / Clinical Assessment** 864 During the baseline and all in-office follow-up visits, a physical examination will be performed and the 865 following data will be collected and recorded: Blood pressure 866 Heart Rate 867 Weight 868 Waist and neck circumference 869 Medications 870 871 6.2.2 **Diet and Physical Activity Counseling** 872 Follow up diet and physical activity counseling by RD 873 Collection of diet and exercise diaries (see attachment) Body composition (Basic metabolic rate, % total body fat, % body water weight, muscle mass 874 875 weight) 6.2.3 **Comorbidities Assessment** 876 877 The following co-morbid conditions will be assessed: diabetes, hypertension, and STOP-BANG score at the 3, 6, 9 and 12 month visits. 878 879 6.2.4 **Blood work** 880 Total 10 ml blood collection for visit 2 and 4 Total 25 ml blood collection for visit 3 and 5 881

Blood Pregnancy (Total Beta Quantitative HCG) (Only applicable for women of childbearing

882

883

potential)

- 884 **BMP**
- 885 HbA1c
- Lipid profile 886
- 887 Amylase
- Lipase 888
- 889 Additional 15 ml blood for future analyses - Banking of additional plasma and serum for future markers of caridometabolic risk in post-RYGB patients (6 and 12 months only). 890

891 6.2.5 **Questionnaires**

- 892 PHO-9
- 893 **IPAQ**

894 6.2.6 **Adverse Events Assessment**

- 895 Through-out the study the occurrence of drug-related AEs and pregnancies will be monitored, recorded,
- and reported to IRB and Novo Nordisk. 896

897 **Monthly Contact** 6.2.7

- 898 Study staff will call or email each subject at 1, 2, 4, 5, 7, 8, 10, and 11 months to review medication compliance and 899 adverse events.
 - 7 Statistical Plan

7.1 **Sample Size Determination**

We intend to recruit 132 subjects. A recent study of liraglutide versus placebo in subjects weighing 106.2 \pm +/- 21.1 kg (BMI 38.2 \pm 6.4) at baseline demonstrated that nearly 2/3 of subjects treated with liraglutide for 56 weeks lost at least 5% of enrollment body weight, vs. approximately 1/4 with placebo. We expect to see similar results in our subjects. In order to detect an absolute difference of 36.1% in the proportion of subjects losing at least 5% of enrollment body weight in the liraglutide (expected proportion 63.2%) and placebo arms (expected proportion 27.1%), with an alpha of 0.05 and beta of 0.1, we will require a sample size of 99 (2x liraglutide: 1x placebo). In order to account for an estimated loss-to-follow-up of 25%, we increase the sample size to 132.

7.2 **Statistical Methods**

Data will be analysed on an intention-to-treat basis. Missing values will be assessed for patterns and imputed using a multiple imputation method for measurements made after baseline. Patient demographics will be summarized by treatment group. Categorical variables will be presented as proportions, normally distributed continuous variables will be presented as mean \pm standard deviation, and skewed continuous variables will be presented as median [interquartile range]. Our primary outcome (proportion of subjects losing at least 5% enrollment body weight) will be assessed using Cochran-Mantel-Haenszel test after accounting for stratification variables. The treatment groups will be further compared by secondary outcomes, using t-tests or Wilcoxon rank sum tests, (as appropriate) for continuous variables. Prior to analysis, non-normally distributed continuous data will be categorized using quartiles or using an appropriate transformation method (e.g. log-transformed).

920 921 922

923

924 925

926

900

901

902

903 904

905

906 907

908

909

910

911 912

913

914

915

916

917

918

919

Paired sample t-tests assessing change at 6 months and 12 months will be used to test, separately for each treatment group, whether each of the post-intervention measurements differs from the baseline measurement. Change in continuous secondary outcome variables will be compared between treatment groups using independent samples t-tests. An ANCOVA model including stratification variables (gender, percent post-operative weight loss) will be used to assess changes in these secondary outcomes. These

927 928	results will provide information to inform further studies, but will remain descriptive given our limited power.
929 930	7.3 Subject Population(s) for AnalysisPrimary and secondary analyses will be performed in the all-treated population.
024	7.4 Interim Analysis
931 932	7.4 Interim Analysis Given the limited duration of the study, we do not plan interim analyses of efficacy parameters.
933	8 Safety and Adverse Events
934	8.1 Definitions
935	8.1.1 Unanticipated Problems Involving Risk to Subjects or Others
936	Any incident, experience, or outcome that meets all of the following criteria:
937	 Unexpected in nature, severity, or frequency
938 939 940	• Related or possibly related to participation in the research (i.e. possibly related means there is a reasonable possibility that the incident experience, or outcome may have been caused by the procedures involved in the research)
941 942	 Suggests that the research places subjects or others at greater risk of harm (including physical, psychological, economic, or social harm).
943	8.1.2 Adverse Event
944	An adverse event (AE) is any symptom, sign, illness or experience that develops or worsens in severity
945	during the course of the study. Intercurrent illnesses or injuries should be regarded as adverse events.
946	Abnormal results of diagnostic procedures are considered to be adverse events if the abnormality:
947	 results in study withdrawal is associated with a serious adverse event
948 949	 is associated with a serious adverse event is associated with clinical signs or symptoms
950	 leads to additional treatment or to further diagnostic tests
951	 is considered by the investigator to be of clinical significance
952	8.1.2.1 Expected Adverse Events related to study drug
953	• Nausea (39.3%)
954	• Diarrhea (20.9%)
955	• Hypoglycemia in Type 2 DM (23.0%)
956	• Constipation (19.4%)
957	• Vomiting (15.7%)
958 050	• Headache (13.6%)
959 960	 Decreased appetite (10.0%) Dyspepsia (9.6%)
960 961	• Fatigue (7.5%)
962	• Dizziness (6.9%)
963	• Abdominal pain (5.4%)
964	• Increased lipase (5.3%)
965	• Upper abdominal pain (5.1%)
966	• Gastroesophageal reflux disease (4.7%)
967	• Gastroenteritis (4.7%)

- Abdominal distension (4.5%)
 Eructation (4.5%)
 Urinary tract infection (4.3%)
 Flatulence (4.0%)
 Viral gastroenteritis (2.8%)
 Injection site erythema (2.5%)
 Injection site reaction (2.5%)
- 975 Insomnia (2.4%)

977

982 983

993

994

996

997 998

999 1000

1001

1010

- Dry mouth (2.3%)
- Asthenia (2.1%)
- **•** Anxiety (1.6%)
- Cholelithiasis (1.5%)
- Hypotension (1.1%)
- Urticaria (0.7%)
 - Breast cancer (0.6%)
 - Cholecystitis (0.6%)
- Colorectal neoplasms (0.5%)
- Pancreatitis (0.3%)
- Cardiac conduction disorder (0.3%)
- Suicidal thoughts (0.2%)
- Papillary thyroid carcinoma (0.2%)
- Angioedema and anaphylactic reaction (reported, but percentage unknown)
- C-cell hyperplasia of thyroid (potential risk)
- Medullary thyroid carcinoma (potential risk)

992 8.1.3 Serious Adverse Event

Adverse events are classified as serious or non-serious. A **serious adverse event** is any AE that is:

- fatal
- life-threatening
 - requires or prolongs hospital stay
 - results in persistent or significant disability or incapacity
 - a congenital anomaly or birth defect
 - suspicion of transmission of infectious agents
 - an important medical event

Important medical events are those that may not be immediately life threatening, but are clearly of major clinical significance. They may jeopardize the subject, and may require intervention to prevent one of the other serious outcomes noted above. For example, drug overdose or abuse, a seizure that did not result in in-patient hospitalization, or intensive treatment of bronchospasm in an emergency department

would typically be considered serious.

All adverse events that do not meet any of the criteria for serious should be regarded as **non-serious** adverse events.

